## **B 5 Review and assessment of potential Hy's law cases**

The instructions in this section should be followed for all cases where PHL criteria are met.

No later than 3 weeks after the biochemistry abnormality was initially detected, the Study Physician contacts the Investigator in order to review available data and agree on whether there is an alternative explanation for meeting PHL criteria other than DILI caused by the IP. The AstraZeneca Global Clinical Lead or equivalent and Global Safety Physician will also be involved in this review together with other patient matter experts as appropriate.

According to the outcome of the review and assessment, the Investigator will follow the instructions below.

If there is an agreed alternative explanation for the ALT or AST and TBL elevations, a determination of whether the alternative explanation is an AE will be made and subsequently whether the AE meets the criteria for a SAE:

- If the alternative explanation is **not** an AE, record the alternative explanation on the appropriate CRF
- If the alternative explanation is an AE/SAE, record the AE /SAE in the CRF accordingly and follow the AZ standard processes

If it is agreed that there is **no** explanation that would explain the ALT or AST and TBL elevations other than the IP:

- Report an SAE (report term 'Hy's Law') according to AstraZeneca standard processes.
  - The 'Medically Important' serious criterion should be used if no other serious criteria apply
  - As there is no alternative explanation for the HL case, a causality assessment of 'related' should be assigned.

If there is an unavoidable delay of over 3 weeks in obtaining the information necessary to assess whether or not the case meets the criteria for HL, then it is assumed that there is no alternative explanation until such time as an informed decision can be made:

- Report an SAE (report term ‘Potential Hy’s Law’) applying serious criteria and causality assessment as per above
- Continue follow-up and review according to agreed plan. Once the necessary supplementary information is obtained, repeat the review and assessment to determine whether HL criteria are met. Update the SAE report according to the outcome of the review amending the reported term if an alternative explanation for the liver biochemistry elevations is determined.

## **B 6 Actions required when potential Hy’s law criteria are met before and after starting study treatment**

This section is applicable to patients with liver metastases who meet PHL criteria on Study treatment having previously met PHL criteria at a study visit prior to starting Study treatment.

At the first on-study treatment occurrence of PHL criteria being met, the Investigator will determine if there has been a significant change in the patients’ condition# compared with the last visit where PHL criteria were met.

- If there is no significant change, no action is required
- If there is a significant change, notify the AstraZeneca representative, who will inform the central Study Team, then follow the subsequent process described in Appendix A 5.
- \*A ‘significant’ change in the patient’s condition refers to a clinically relevant change in any of the individual liver biochemistry parameters (ALT, AST or total bilirubin) in isolation or in combination, or a clinically relevant change in associated symptoms. The determination of whether there has been a significant change will be at the discretion of the Investigator, this may be in consultation with the Study Physician if there is any uncertainty.

## **B 7 Actions required for repeat episodes of potential Hy’s law**

This section is applicable when a patient meets PHL criteria on study treatment, and has already met PHL criteria at a previous on study treatment visit.

The requirement to conduct follow-up, review, and assessment of a repeat occurrence(s) of PHL is based on the nature of the alternative cause identified for the previous occurrence.

The Investigator should determine the cause for the previous occurrence of PHL criteria being met and answer the following question:

Was the alternative cause for the previous occurrence of PHL criteria being met found to be the disease under study (eg, chronic or progressing malignant disease, severe infection or liver disease)

If **No**: Follow the process described in Appendix B4.1

If **Yes**: Determine if there has been a significant\* change in the patient's condition compared with when PHL criteria were previously met.

If there is no significant change, no action is required.

If there is a significant change, follow the process described in Appendix B4.

\*A 'significant' change in the patient's condition refers to a clinically relevant change in any of the individual liver biochemistry parameters (ALT, AST or total bilirubin) in isolation or in combination, or a clinically relevant change in associated symptoms. The determination of whether there has been a significant change will be at the discretion of the Investigator; this may be in consultation with the Study Physician if there is any uncertainty.

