#### **Hy's law (HL)**

AST or ALT  $\geq 3 \times$  ULN together **with** TBL  $\geq 2 \times$  ULN, where no other reason, other than the IP, can be found to explain the combination of increases, eg, elevated ALP indicating cholestasis, viral hepatitis, another drug.

For PHL and HL the elevation in transaminases must precede or be coincident with (ie, on the same day) the elevation in TBL, but there is no specified time frame within which the elevations in transaminases and TBL must occur.

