### **B 3 Identification of potential Hy's law cases**

In order to identify cases of PHL it is important to perform a comprehensive review of laboratory data for any patient who meets any of the following identification criteria in isolation or in combination:

- ALT  $\geq 3 \times$  ULN
- AST  $\geq 3 \times$  ULN
- TBL  $\geq 2 \times$  ULN

The Investigator will without delay review each new laboratory report and if the identification criteria are met will:

- Determine whether the patient meets PHL criteria (see Appendix B2 for definition) by reviewing laboratory reports from all previous visits
- Promptly enter the laboratory data into the laboratory CRF

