### **B 4 Follow-up**

#### **B 4.1 Potential Hy's law criteria not met**

If the patient does not meet PHL criteria the Investigator will:

- Perform follow-up on subsequent laboratory results according to the guidance provided in the Clinical Study Protocol.

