#### **B 4.2 Potential Hy's law criteria met**

If the patient does meet PHL criteria the Investigator will:

- Determine whether PHL criteria were met at any study visit prior to starting study treatment (See Section 7.4 Safety Reporting)
- Notify the AstraZeneca representative who will then inform the central Study Team

The Study Physician contacts the Investigator, to provide guidance, discuss and agree an approach for the study patients' follow-up and the continuous review of data. Subsequent to this contact the Investigator will:

- Monitor the patient until liver biochemistry parameters and appropriate clinical symptoms and signs return to normal or baseline levels, or as long as medically indicated

- Investigate the etiology of the event and perform diagnostic investigations as discussed with the Study Physician.
- If at any time (in consultation with the Study Physician the PHL case meets serious criteria, report it as an SAE using standard reporting procedures.

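### Appendix B7 sends some repeat potential Hy's law episodes to the process for patients who do not meet the criteria (B4.1 instead of B4.2)

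*Protocol*

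**What the plan says.** Appendix B7 of the protocol sets its own scope: "This section is applicable when a patient meets PHL criteria on study treatment", having already met the criteria at an earlier on-treatment visit. It says that the need to follow up, review and assess the repeat "is based on the nature of the alternative cause identified for the previous occurrence". It then asks whether the earlier episode was attributed to the disease under study and gives three outcomes:

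- No: "Follow the process described in Appendix B4.1".
- Yes, without a significant change in the patient's condition: nothing further is required.
- Yes, with a significant change: follow Appendix B4.

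Appendix B4 has two subsections. B4.1 opens "If the patient does not meet PHL criteria the Investigator will" and lists one action, routine follow-up of later laboratory results. B4.2 is for patients who do meet PHL criteria. Its listed actions include "Notify the AstraZeneca representative who will then inform the central Study Team" and, after the Study Physician has made contact and an approach has been agreed, "Investigate the etiology of the event and perform diagnostic investigations as discussed with the Study Physician".

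**The concern.** The 'No' branch points to a subsection whose opening condition is false for every patient in B7. It also runs against the section's own logic. B7 lightens the handling of one group only, namely disease-attributed repeats with no significant change. A 'No' answer means that the disease did not explain the earlier episode. The cause may then have been, for example, another drug, which is among the alternative explanations in the Hy's law definition in B2 ("elevated ALP indicating cholestasis, viral hepatitis, another drug"), or the investigational product itself. As printed, these patients get a lighter instruction than patients whose earlier episode was attributed to the disease and whose condition has since changed.

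What is at stake is prompt sponsor awareness of a new liver episode. Section 2.2.2.1 lists hepatitis and raised transaminases as durvalumab risks, and Section 7.5 lists hepatitis among the immune-mediated events. Section 2.1.4 reports one death from hepatotoxicity, classed as immune-mediated, in the durvalumab plus chemotherapy arm of the earlier phase 3 trial.

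**Working it through.** No arithmetic beyond counting applies, so the check is to trace the cross-references.

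**Step 1: does B4.1 fit anyone in B7?** B7 requires that PHL criteria are met now. B4.1 requires that they are not met. The two conditions exclude each other, so B4.2 is the only part of B4 that a B7 patient can enter.

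**Step 2: which B7 outcomes are affected?**

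- No → B4.1: wrong subsection.
- Yes, no significant change → no action: consistent with B7's stated rule.
- Yes, significant change → B4: not an error, because B4 sorts a patient who meets PHL criteria to B4.2.

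One of three outcomes is misdirected. This counts branches and does not measure how many patients are involved.

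**Step 3: what does the wrong pointer leave out?** B4.2 lists five investigator actions. For each, the question is whether another provision covers it when B4.1 is followed.

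1. Check whether PHL criteria were met before treatment: already due at the first on-treatment episode.
2. Notify the sponsor's representative: no equivalent explicit step in B4.1. B3 requires the investigator to "Determine whether the patient meets PHL criteria (see Appendix B2 for definition) by reviewing laboratory reports from all previous visits" and to enter the data promptly in the case report form, but it does not require notification.
3. Monitor until values return to normal or baseline: partly covered by B4.1's laboratory follow-up. Table 2 also schedules clinical chemistry throughout treatment, and its note h requires liver results to be reviewed before each infusion.
4. Investigate the cause: covered in general terms by Sections 7.9 and 7.9.1, which require evaluation for alternative causes, and by B5, which requires agreement on whether anything other than drug-induced injury explains the case.
5. Report as an SAE if serious: required by Section 6.3.1 (text after Table 5) and Section 7.4.

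Four of the five are covered elsewhere at least in part, so 5 − 4 = 1 is distinctly omitted: notification. With it go the Study Physician contact that it sets off and the diagnostic plan agreed at that contact.

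**Step 4: do other provisions make the pointer right?** None does. B5 applies to every case meeting PHL criteria, which mitigates the error without making B4.1 the correct destination.

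**Step 5: the neighbouring pointer.** B6 tells the investigator to notify the sponsor's representative after a significant change and then to follow Appendix A 5. That appendix defines important medical events and contains no liver follow-up process. This is a separate slip, and the B7 point does not depend on it.

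**The case against.** The strongest reply is that the error exposes itself. An investigator who turns to B4.1 sees at once that its condition does not fit, and the right process is the next subsection. B4.2 and B5 also apply to these patients by their own wording, and B5 has the Study Physician contact the investigator within three weeks of detection in any case. B1 says that Appendix B is not the guide to managing liver abnormalities and refers that to the toxicity management guidelines. The sponsor was already involved at the first episode.

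Most of this stands, and it limits the consequence. Three gaps remain. First, the B5 contact depends in practice on the sponsor learning of the case, and B4.2 is where that notification is written. Second, B7 makes follow-up and review of repeats conditional on its own branches, so a site could treat it as the specific rule that displaces the general ones. Third, involvement at the first episode does not announce a second one, because B4.2 monitoring may end once values have returned to normal or baseline.

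A reader might infer more: that repeat cases escape medical review, or that the search for a cause is dropped. The documents do not support either. B5 covers all PHL cases, and Sections 7.9 and 7.9.1 require evaluation for other causes independently of Appendix B.

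**Conclusion.** The cross-reference is wrong as written and should be corrected. The consequence is narrow. For a repeat episode whose predecessor was not attributed to the disease under study, a literal reading drops the explicit notification of the sponsor's representative and the Study Physician contact and agreed diagnostic plan that follow from it. It is a conflict between instructions on liver safety, not a proven loss of review or monitoring.

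Few patients are likely to be affected, since each must meet PHL criteria at least twice on treatment with the earlier episode put down to something other than the disease. The protocol gives no expected number. The 'No' group may be narrower than it first appears, because B7's examples of disease under study extend to severe infection and liver disease; another drug or the investigational product are the clearer 'No' cases. How many such patients would still be on treatment depends on the toxicity management guidelines, which are not part of the document reviewed. Sample size, endpoint definitions and analyses are unaffected.

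**What to change.** In the 'No' branch of Appendix B7, replace the reference to B4.1 with B4.2, and notify sites. B5 need not be added, because it already applies to every case meeting PHL criteria. In the same edit, change the B6 reference to Appendix A 5 so that it points to the steps of B4.2 that follow notification, and to B5. The reference to B4 in B7's 'Yes' branch can stay; naming B4.2 there would be a clarification only.

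The cost is two corrected references and a site notice. Data collection, sample size and analyses do not change.

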## Appendix C Guidelines for Evaluation of Objective Tumor Response

### Guidelines for Evaluation of Objective Tumor Response Using RECIST 1.1 Criteria (Response Evaluation Criteria in Solid Tumors)

#### Introduction

This appendix details the implementation of Response Evaluation Criteria in Solid Tumors (RECIST) 1.1 guidelines (Eisenhauer et al 2009) for the study with regards to Investigator assessment of tumor burden including protocol-specific requirements for this study.

#### Definition of measurable, non-measurable, target and non-target lesions

Only patients with measurable target disease at baseline should be included in the study.

Measurable disease is defined by the presence of at least one measurable lesion which has not been previously irradiated.

Tumor lesions selected for screening biopsy should not be selected as target lesions, unless imaging occurred at least 2 weeks after biopsy, allowing time for healing.

#### Measurable:

A lesion, not previously irradiated or biopsied per the protocol prior to randomisation, that can be accurately measured at baseline as  $\geq 10$  mm in the longest diameter (except lymph nodes which must have short axis  $\geq 15$  mm) with computed tomography (CT) or magnetic resonance imaging (MRI) and which is suitable for accurate repeated measurements.

#### Non-measurable:

- All other lesions, including small lesions (longest diameter  $< 10$  mm or pathological lymph nodes with  $\geq 10$  mm to  $< 15$  mm short axis at baseline).
- Truly non-measurable lesions include the following: bone lesions, leptomeningeal disease, ascites, pleural/pericardial effusion, inflammatory breast disease, lymphangitic involvement of skin or lung and, abdominal masses/abdominal organomegaly identified by physical examination that is not measurable by CT or MRI.
- Tumour lesions selected for screening biopsy
- Previously irradiated lesions

---

 The short axis is defined at the longest axis perpendicular to the long axis of the tumour. Nodes with  $< 10$  mm short axis are considered non-pathological and should not be recorded or followed as non-target lesions (NTLs).

 Localised post-radiation changes which affect lesion sizes may occur. Therefore, lesions that have been previously irradiated will not be considered measurable and must be selected as NTL at baseline and followed up as part of the NTL assessment.

- Skin lesions assessed by clinical examination
- Brain metastasis

**Special cases:**

- Lytic bone lesions or mixed lytic–blastic lesions, with identifiable soft tissue components, can be considered measurable if the soft tissue component meets the definition of measurability. Blastic lesions are considered non-measurable.
- Cystic metastases can be considered measurable lesions if they meet the criteria for measurability from a radiological point of view, but if non-cystic lesions are present in the same patient, these should be selected as target lesions (TLs).

**Target lesions:**

A maximum of 5 measurable lesions (with a maximum of 2 lesions per organ), representative of all lesions involved suitable for accurate repeated measurement, should be identified as TLs at baseline. Lymph nodes, in any location, are collectively considered as a single organ, with a maximum of 2 lymph nodes as TLs. A bilateral organ is considered as a single organ.

**Non-target lesions:**

All other lesions (or sites of disease) not recorded as TL should be identified as NTL at baseline.

**Methods of assessment**

**The same method of assessment and the same technique should be used to characterize each identified and recorded lesion at baseline and during follow-up visits.**

A summary of the methods to be used for RECIST assessment is provided in Table 10 , and those excluded from tumor assessments for this study are highlighted with the rationale provided.

**Table 10 Summary of methods of assessment**

| Target lesions | Non-target lesions | New lesions   |
|-----------------------|---------------------------|----------------------|
| CT (preferred)        | CT (preferred)            | CT (preferred)       |
| MRI                   | MRI                       | MRI                  |
|                       | Clinical examination      | Clinical examination |
|                       | X-ray, Chest X-ray        | X-ray, Chest X-ray   |
|                       |                           | Ultrasound           |
|                       |                           | Bone scan            |
|                       |                           | FDG-PET              |

CT Computed tomography; FDG-PET 18-Fluoro-deoxyglucose positron emission tomography; MRI Magnetic resonance imaging.

### **CT and MRI**

CT and MRI, each preferably with intravenous contrast, are generally considered to be the best currently available and reproducible methods to measure TL selected for response assessment and to assess NTL and identification of any new lesions.

It is recommended that intravenous contrast-enhanced CT examinations of the chest and abdomen (including liver and adrenal glands) are used to assess tumour burden at baseline and follow-up visits. Any other areas of disease involvement should be additionally imaged based on the signs and symptoms of individual patients. In patients who are sensitive to intravenous CT contrast, a non-contrast CT examination of the chest and an MRI with intravenous contrast of the abdomen and pelvis is appropriate. In patients with severely compromised renal function a non-contrast CT examination of the chest, abdomen and pelvis is appropriate. For brain lesion assessment, MRI with intravenous contrast is the preferred method over contrast-enhanced CT. It is strongly recommended to maintain use of the same imaging modality (CT or MRI), acquisition protocol, facility and scanner across all imaging timepoints per patient.

### **Clinical examination**

Clinical examination will not be used for assessment of TL. Clinically detected lesions can be selected as TLs if they are assessed by CT or MRI scans. Clinical examination can be used to assess NTL and to identify the presence of new lesions.

### **X-ray**

#### **Chest X-ray**

Chest X-ray assessment will not be used for assessment of TL as they will be assessed by CT examination or MRI examination. Chest X-ray can, however, be used to assess NTL and to identify the presence of new lesions.

#### **Plain X-ray**

Plain X-ray may be used as a method of assessment for bone NTL and to identify the presence of new bone lesions.

### **Ultrasound**

Ultrasound examination will not be used for assessment of TL and NTL as it is not a reproducible method, does not provide an accurate assessment of tumor size, and it is subjective and operator dependent. Ultrasound examination can, however, be used to identify the presence of new lesions. If new clinical symptoms occur and an ultrasound is performed then new lesions should be confirmed by CT or MRI examination.

### **Endoscopy and laparoscopy**

Endoscopy and laparoscopy will not be used for tumor assessments as they are not validated in the context of tumor assessment.

### **Tumor markers**

Tumor markers will not be used for tumor response assessments as per RECIST 1.1.

### **Cytology and histology**

Histology will not be used as part of the tumor response assessment as per RECIST 1.1.

Cytological confirmation of the neoplastic origin of any effusion that appears or worsens during treatment is required when the measurable tumour has met criteria for response or stable disease. In such circumstances, the cytology is necessary for the Investigator to differentiate between response/stable disease (an effusion may be a side effect of the treatment) and progressive disease (if the neoplastic origin of the fluid is confirmed). Where cytology findings are not available, any effusion that significantly worsens (from trace to large) or appearance of clinically significant effusion (requiring change in drug therapy) during the study treatment will be considered to be progression of NTL, or disease progression due to new lesions.

### **Isotopic bone scan**

Bone lesions identified on an isotopic bone scan at baseline and confirmed by CT, MRI, or X-ray at baseline should be recorded as NTL and followed by the same method as per baseline assessment.

Isotopic bone scans may be used as a method of assessment to identify the presence of new bone lesions at follow-up visits. New lesions will be recorded where a positive hot-spot that was not present on the baseline bone scan assessment is identified on a bone scan performed at any time during the study. The Investigator should consider the positive hot-spot to be a significant new site of malignant disease and represent true disease progression in order to record the new lesion. Confirmation by CT, MRI and X-ray is recommended where bone scan findings are equivocal.

